### Lesion visualization (on site read)

The same analyses as lesion visualization co-primary criteria (off-site) on matching and non-matching lesions will be performed.

## Improvement in patient-level lesion visualization scores, paired versus pre-contrast images

Improvement in patient-level lesion visualization scores, paired versus pre-contrast images. Improvement in patient-level lesion visualization will be calculated from the 3 co-primary criteria by reader and will be tabulated by contrast agent groups; off-site and on-site reader's outcomes will be separately presented using FAS 1 and FAS 2 for off-site outcomes and extended FAS 1 and extended FAS 2 for on-site outcomes.

### Lesion visualization at lesion level (off site read)

Each lesion visualization criterion will be analyzed by reader using a general linear model, modelling the lesion score as a function of the reader, center, period and on the one hand contrast agent group (GBCA: gadopiclenol and gadobutrol) with repeated measures on the lesion due to the pairing of contrast agents in lesions and on the other hand, modality of the MRI (pre and paired images) with repeated measures on the lesion due to the pairing of MRI modalities or contrast agent group in lesions. Matching and no matching lesions will be kept in the analysis.

Hence the models will be the following for gadobutrol vs. gadopiclenol:

- Border delineation = contrast agent group + period + reader + center + error
- Internal morphology = contrast agent group + period + reader + center + error
- Degree of contrast enhancement = contrast agent group + period + reader + center + error

and the following for pre vs. paired within gadopiclenol MRI period:

- Border delineation = MRI modality + period + reader + center + error
- Internal morphology = MRI modality + period + reader + center + error
- Degree of contrast enhancement = MRI modality + period + reader + center + error

The parameters of the general linear model will be estimated using the SAS® procedure Mixed. The procedure used for the analysis will be the following for each criterion:

proc mixed data = XXX method = REML;

class lesion # GBCA (or MRI modality) period reader center;

model eval = GBCA(or MRI modality) period reader center;

repeated GBCA(or MRI modality) / subject=lesion # / type = cs;

/\* To get the estimate and the corresponding confidence interval of the paired difference \*/

```

proc mixed data = XXX method = REML;
  class lesion_# GBCA (or MRI modality) period reader center organ;
  model eval = GBCA (or MRI modality) period reader center organ;
  repeated GBCA (or MRI modality) / subject=lesion_# / type = cs;
/* To get the estimate and the corresponding confidence interval of the paired difference */
  lsmeans GBCA (or MRI modality);
  lsmeans GBCA (or MRI modality) * organ
  estimate "gadopiclenol - gadobutrol" GBCA (or "Paired - Pre" MRI modality) 1 -1 /cl;
  estimate "gadopiclenol - gadobutrol" GBCA (or "Paired - Pre" MRI modality) *organ ... /cl;
run;

```

The Student's t-based 95% confidence intervals of the difference between gadopiclenol and gadobutrol will be constructed for each of 3 lesion visualization criteria for each body region/organ using the FAS2 on all lesions.

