A concordance reading process (lesion tracking) will be performed as an independent off-site procedure. The purpose is to guarantee an unambiguous assignment (matching) of the lesions between modalities (Pre and Paired images) of the same MR examination, between two MR examinations for the same patient, and among 3 readers. Lesion tracking will be carried out by another independent radiologist (so-called concordance reader) in blinding condition (except the ID number of lesions) on the basis of the off-site readers' assessments. Once the concordance process is done, a correspondence/tracking lesion table should be obtained, so that lesions could be compared for analysis within readers or for the inter- and intra-reader (refer to trial "Blinded Image Evaluation Charter" for details).

8.4.10 ***Image Archive and Final Deliverables***

All imaging data will be maintained in a secure environment. The Imaging Core Laboratory will maintain a centralized image archive that will contain every imaging examination received from the clinical investigators for the trial. Measurements will also be stored so that these data may be audited if necessary. A copy of images transferred by the investigators to Imaging Core Laboratory will be transferred to Guerbet after database lock for archiving.

 CONFIDENTIAL	Protocol No. GDX-44-011 Version No. 3.0 (including amendment 2) June 30, 2020	Page 52 / 82
--	---	--------------

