#### **4. CHANGES IN THE CONDUCT OF THE TRIAL OR PLANNED ANALYSES**

Protocol was amended during the course of the trial to increase the sample size from 250 to 300 patients (amendment 2).

Indeed, 200 evaluable patients (defined as patients who completed the trial and with a valid primary criterion) are to be secured to allow a sufficient statistical power to meet both study primary objectives. The initial sample size calculation was based on a non-evaluable patient rate (drop-out rate and non-valid primary criterion rate) of 20% (50 patients), leading to a target of 250 enrolled patients.

Based on 245 patients currently enrolled (98% of planned target), 25 patients are already dropped-out. This drop-out rate is partially due to the Covid-19 pandemic preventing 6 patients from completing the trial up to now. Furthermore, Covid-19 pandemic may continue to impact enrollment of patients and/or protocol compliance.

In addition, the current estimated number of patients with no valid primary criterion is about 68 patients.

Altogether, this current estimation of 93 (25+68) non-evaluable patients is expected to increase before the recruitment completion. As a consequence, the revised hypothesis for the non-evaluable patient rate is now about 33%.

Three additional datasets will be defined and used for secondary efficacy analyses.

Five supplemental secondary analysis of lesion visualization criteria will be conducted in addition of those described in the final Protocol Version N° 3.0 (including amendment 2) dated June 30, 2020 and the amendment for FRANCE dated June 30, 2020:

- An analysis will be performed globally. Mixed model will be considered with patient and reader as adjustment factors.
- An analysis will be performed including non-matching lesions. Mixed model will be considered by reader with patient as adjustment factor.
- Two analyses will be performed at lesion level.
  - Plain: Mixed model will be considered by reader with patient and site as adjustment factors.
  - Lesion size based: Mixed model will be considered by reader with size of lesion, patient and site as adjustment factors.
- Additional subgroup analyses will be performed considering main demographic parameters (age, sex, race, ethnicity and geographic region) and MRI machine field (1.5 tesla and 3 tesla) for the 3 co-primary criteria.

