## Lesion size analysis for lesion visualization at lesion level (off site read)

Lesion visualization at lesion level (off site read) analysis comparing the two GBCA will be repeated with size of lesion added as co-factor. Size will be classified as following:

- $=<1$  cm
- $>1$  cm and  $=<2$  cm
- $>2$  cm

Hence the models will be the following:

- Border delineation = contrast agent group + period + reader + center + class\_size + error
- Internal morphology = contrast agent group + period + reader + center + class\_size + error
- Degree of contrast enhancement = contrast agent group + period + reader + center + class\_size + error

The parameters of the general linear model will be estimated using the SAS® procedure Mixed. The procedure used for the analysis will be the following, for each criterion:

```

proc mixed data = XXX method = REML;
  class lesion_# GBCA period reader center class_sized;
  model eval = GBCA period reader center class_sized;
  repeated GBCA / subject=lesion_# / type = cs;
/* To get the estimate and the corresponding confidence interval of the paired difference */
  lsmeans GBCA;
  lsmeans GBCA* class_sized
  estimate "gadopiclenol - gadobutrol" GBCA 1 -1 /cl;
  estimate "gadopiclenol - gadobutrol" GBCA* class_sized ... /cl;
run;

```

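### The lesion-level models are specified by reader with a patient factor in SAP section 4, but SAP 5.6.2 makes reader a model term, omits patient, and prints a program unsuited to a single run over three readers

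*SAP*

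**What the plan says.** **SAP section 4** adds two lesion-level analyses to those in the protocol. The first is specified as "Plain: Mixed model will be considered by reader with patient and site as adjustment factors". The second has the same form, again run separately for each reader, and adds lesion size to those two factors.

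The same list has a separate global analysis, in which patient and reader are both adjustment factors.

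**SAP 5.6.2, lesion visualization at lesion level**, begins: "Each lesion visualization criterion will be analyzed by reader using a general linear model, modelling the lesion score as a function of the reader, center," followed by period and agent or modality. The equations for all three criteria and both comparisons (six in total) carry reader, for example "Border delineation = contrast agent group + period + reader + center + error". Reader is in CLASS and MODEL, and patient is nowhere. The code is introduced with "The procedure used for the analysis will be the following for each criterion". The REPEATED effect is contrast agent (or MRI modality) and the subject is `lesion_#`, with compound symmetry. Matching and non-matching lesions are both kept.

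**SAP 5.6.2, lesion size analysis**, repeats the structure with a size class: "model eval = GBCA period reader center class_sized".

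**Protocol 8.4.9** says that lesion tracking assigns lesions between modalities, "between two MR examinations for the same patient, and among 3 readers". The SAP does not define `lesion_#`.

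**The concern.** SAP 3.1 has a contract organisation run the analysis from this document, so the printed code is its instruction. On this text a programmer could produce three reader-specific estimates, one pooled estimate, or a fit that breaks down. Each is defensible from some sentence of the SAP.

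The choice matters for interpretation. Both primary objectives are judged by a rule of two readers out of three, and only reader-specific lesion-level results can be set beside that rule. If the choice is left until programming, it may be made with results in view.

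Error bars are also at stake. The pooled program has no structure for several readers of one lesion, and on either run unit there is no term for several lesions of one patient.

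**Working it through.** The documents give no figure for this point, so there is none to reproduce. The check compares the texts and then works through the covariance structure.

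**1. How the SAP marks the run unit elsewhere.** In 5.6.1 both primary programs are introduced as run for each co-primary criterion and each off-site reader. Under Number of lesions (5.6.2) each off-site reader has its own model. Under Global model (5.6.2) pooling is marked by entering reader as a covariate in a single model. The lesion-level equations and code have the pooled form, while section 4 and the opening words of the lesion-level text have the by-reader form.

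**2. Pooled run, lesion identifier shared among readers.** Inputs: three readers per case (5.6.2, Inter-reader variability), lesions matched among readers (Protocol 8.4.9), and a repeated effect with two levels. A lesion then has up to 3 × 2 = 6 rows on two levels. Two rows of the same lesion and agent from different readers occupy the same level, so their modelled correlation is 1. With assumed within-lesion correlation ρw of 0.2, 0.5 and 0.8:

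| Readers per lesion | Block | Rank | Determinant |
|---|---|---|---|
| 3 | 6 × 6 | 2 | 0 at every ρw |
| 2 | 4 × 4 | 2 | 0 at every ρw |
| 1 | 2 × 2 | 2 | 1 − ρw² = 0.96, 0.75, 0.36 |

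With two or more readers on a lesion the block is singular and the REML likelihood is undefined.

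**3. Pooled run, lesions numbered within reader.** The model now fits but treats reads of one lesion as different lesions. Let each reader's agent difference have variance s², with correlation ρ between readers. The mean over k readers has variance (s²/k)(1 + (k − 1)ρ), whereas the model uses s²/k. True SE divided by model SE is therefore sqrt(1 + (k − 1)ρ). The values of ρ are assumed.

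| ρ | k = 3: sqrt(1+2ρ) | k = 2: sqrt(1+ρ) | k = 1 |
|---|---|---|---|
| 0.2 | 1.18 | 1.10 | 1 |
| 0.4 | 1.34 | 1.18 | 1 |
| 0.6 | 1.48 | 1.26 | 1 |

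For k = 3, nominal 95% intervals would cover about 90%, 86% and 81%, from 2Φ(1.96/ratio) − 1. At ρ = 0.5 the ratio is 1.41 and the formula gives 83.4%; a simulation of 4,000 trials with 300 lesions each gave 82.8%.

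**4. Run by reader.** There is one row per lesion and agent, which is the last row of the table in step 2, and REPEATED works. Reader is constant: a design with intercept, agent and reader has 3 columns and rank 2, so the term does nothing. Up to three lesions of one patient still enter as separate subjects with no patient term. For m lesions per patient whose agent differences have correlation r, the same algebra gives sqrt(1 + (m − 1)r), which is sqrt(1 + 2r) for three lesions and 1 for one.

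**The case against.** The best defence is that every prose statement says by reader, including the sentence that opens the lesion-level text in 5.6.2. If the prose governs, the REPEATED statement works and the reader term is only redundant. The evidence for pooling is not conclusive. The SAP's run-unit wording is uneven: E% is tabulated for each reader, yet its program is introduced without naming one. The primary programs have no BY statement either. The table for the global model is labelled as pooled, whereas Tables 14.2.2.10 to 14.2.2.17 are not. This stands, and it means that the documents do not establish a pooled run.

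Two related objections also stand. The singular covariance needs pooling together with a shared identifier, and such a fit would break down visibly rather than report a wrong answer. The silent error needs pooling together with within-reader numbering, and the k = 3 ratio is an upper bound because readers choose lesions separately and non-matching ones are kept.

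Reader might also mean the individual radiologist inside a composite Reader 1, 2 or 3 (SAP 1.2). The term would then not be redundant, but neither lesion-level text says so.

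Finally, reader disagreement is visible elsewhere, in the per-reader primary results and the inter-reader analysis. That limits the harm. It does not settle which lesion-level model will be run or supply the missing patient factor.

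**Conclusion.** The inconsistency is real. Section 4 gives reader-specific models with patient and site, while 5.6.2 says by reader, models reader as a factor and omits patient. The printed program is unsuitable if run once over all readers and incomplete if run by reader.

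- **Pooled, shared identifier:** singular covariance, no valid fit.
- **Pooled, within-reader numbering:** standard errors understated by up to 1.18, 1.34 and 1.48 at assumed ρ of 0.2, 0.4 and 0.6, and by less for lesions scored by fewer than three readers.
- **By reader:** no problem from reader, but up to sqrt(1 + 2r) from unmodelled lesions within patient, with r unknown.

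A reader might infer that 5.6.2 simply prescribes a pooled model that must fail. The text does not support that, because the section itself says by reader and leaves `lesion_#` undefined. Nor does it follow that running by reader cures everything, since the patient factor is still missing. Nor is the trial's main conclusion in question: these are supplemental secondary analyses with no success rule, and the two primary analyses are separately specified and unaffected.

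**What to change.** Bring 5.6.2 into line with section 4, in both the lesion-level and the lesion-size texts:

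- Remove reader from the equations, CLASS and MODEL, and state that each program is run separately for Readers 1, 2 and 3. If an adjustment for the individual radiologist within a composite reader was meant, say so.
- Define `lesion_#` so that it identifies one lesion within one patient, and nest it in patient in the SUBJECT option so that equal numbers in different patients are not merged.
- Add the patient factor that section 4 requires, for example as a random effect. A patient intercept cancels from within-lesion differences of matched lesions, so the SAP should also say whether a patient-by-agent (or patient-by-modality) term is included. That term is what represents correlated agent differences among one patient's lesions.
- Report Tables 14.2.2.10 to 14.2.2.17 and Figures 14.2.2.1 to 14.2.2.4 per reader.

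The cost is a wording and code change, more columns per table, and less precision per estimate than pooling would give. If a pooled model is preferred, section 4 must change, and the covariance must separate readers within lesion, for example through a reader-by-agent repeated effect.

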## Lesion size analysis for lesion visualization at lesion level (off site read)

Lesion visualization at lesion level (off site read) analysis comparing the two GBCA will be repeated with size of lesion added as co-factor. Size will be classified as following:

- $=<1$  cm
- $>1$  cm and  $=<2$  cm
- $>2$  cm

Hence the models will be the following:

- Border delineation = contrast agent group + period + reader + center + class\_size + error
- Internal morphology = contrast agent group + period + reader + center + class\_size + error
- Degree of contrast enhancement = contrast agent group + period + reader + center + class\_size + error

The parameters of the general linear model will be estimated using the SAS® procedure Mixed. The procedure used for the analysis will be the following, for each criterion:

```

proc mixed data = XXX method = REML;
  class lesion_# GBCA period reader center class_sized;
  model eval = GBCA period reader center class_sized;
  repeated GBCA / subject=lesion_# / type = cs;
/* To get the estimate and the corresponding confidence interval of the paired difference */
  lsmeans GBCA;
  lsmeans GBCA* class_sized
  estimate "gadopiclenol - gadobutrol" GBCA 1 -1 /cl;
  estimate "gadopiclenol - gadobutrol" GBCA* class_sized ... /cl;
run;

```

## Technical adequacy of images

The quality of images will be assessed by off-site readers and on-site radiologists. Technical adequacy and assessable status of images and will be tabulated by contrast agent groups and MRI modalities (pre and paired) using All Randomized Set; off-site and on-site reader's outcomes will be separately analyzed. Non assessable reasons will be only listed.

### Number of lesions

The number of lesions by patient will be assessed by off-site readers and on-site radiologists and will be tabulated (as quantitative parameter and in class: No lesion / 1 lesion / 2 lesions / 3 lesions / More than 3

CONFIDENTIAL	STATISTICAL ANALYSIS PLAN PHASE III TRIAL GDX-44-011 VERSION NO. 2.0      DATED 25 JANUARY 2021	████████ Page 36 / 57
--------------	---	--------------------------

lesions) by contrast agent groups and MRI modalities (pre and paired); off-site and on-site reader's outcomes will be separately analyzed. Matching and no matching lesions will be kept in the analysis.

The number of lesions will be fitted by a multivariate model using the negative binomial distribution. The model will include the factors period contrast agent group and MRI modalities (pre and paired). Each off-site reader will be analyzed by a specific model and on-site reading will be analyzed in the same way. The parameters of the model will be estimated using the SAS® procedure Glimmix. The difference between contrast agent groups using extended FAS2 and between MRI modalities using extended FAS1 in mean of lesions detected and associated 95% CI will be computed.

Procedure used will be the following for each off-site reader and on-site reading:

Paired vs Pre analysis in Gadopiclenol group using extended FAS1:

```
proc glimmix data = XXX;
  class subject MRI period;
  model nblesions = MRI period / dist = negbin link = id;
  random _residual_ / subject = subject;
  lsmeans MRI/ pdiff = controlu('PRE') tdiff cl alpha = 0.025;
  lsmeans MRI;
  estimate "Paired - Pre" MRI 1 -1 /cl;
run;
```

Paired Gadopiclenol vs Paired Gadobutrol using extended FAS2:

```
proc glimmix data = XXX;
  class subject GBCA period;
  model nblesions = GBCA / dist = negbin link = id;
  random _residual_ / subject = subject;
  lsmeans GBCA / pdiff = controlu('gadobutrol') tdiff cl alpha = 0.025;
  lsmeans GBCA;
  estimate "gadopiclenol - gadobutrol" GBCA 1 -1 /cl;
run;
```

Subgroup analyses by body region and organ as described in the section additional analysis of the primary criteria will be conducted for number of lesions.

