7 EVALUATION CRITERIA

An overview of the imaging trial criteria evaluated by the investigator (INV) and the Independent Blinded Readers (IBR) is provided in the [Table 2](#) below:

Table 2: Overview of imaging trial criteria

Images	Pre gadopiclenol	Pre gadobutrol	Paired gadopiclenol	Paired gadobutrol	Global matched-pairs
Lesion visualization	INV/IBR	INV/IBR	INV/IBR	INV/IBR	
Technical adequacy of images	INV/IBR	INV/IBR	INV/IBR	INV/IBR	
Number, size and location of lesions	INV/IBR	INV/IBR	INV/IBR	INV/IBR	
Diagnostic confidence	INV/IBR	INV/IBR	INV/IBR	INV/IBR	
Impact of contrast-enhanced MRI on patient treatment plan			INV	INV	
Percentage enhancement (E%) of lesion			IBR	IBR	
Lesion to Background Ratio (LBR)			IBR	IBR	
Overall diagnostic preference					IBR

INV: Investigator (on-site)

IBR: Independent Blinded Readers (off-site)

The image sets evaluated per patient are described in the [Table 3](#) below:

Table 3: Images sets per patient

Image Set Number	Type
1a	Pre images = unenhanced MRI before gadopiclenol injection
2a	Pre images = unenhanced MRI before gadobutrol injection
1b	Paired images = combined unenhanced and gadopiclenol-enhanced MRI (pre+post images)
2b	Paired images = combined unenhanced and gadobutrol-enhanced MRI (pre+post images)

 CONFIDENTIAL	Protocol No. GDX-44-011 Version No. 3.0 (including amendment 2) June 30, 2020	Page 38 / 82
---	---	--------------

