**Impact of contrast-enhanced MRI on patient treatment plan**

The impact on patient treatment plan will be tabulated by contrast agent groups. The therapeutic management proposed based on combined unenhanced and contrast-enhanced MRI vs the one based on unenhanced MRI will be tabulated for all patients having the treatment plan be changed.

The impact on patient treatment plan will be tabulated by contrast agent groups and tumor classification before GBCA administration.

The tumor classification is based on diagnosis done at unenhanced MRI according to the following:

Diagnosis	Tumor classification
Negative	Non Malignant
Benign	Non Malignant
Probably Benign finding	Non Malignant
Low Suspicion of Malignancy	Malignant
Intermediate Suspicion of Malignancy	Malignant
Moderately High Suspicion of Malignancy	Malignant
Not assessable	Not assessable

The impact on patient treatment plan will be fitted by a multiple logistic regression model for correlated data. The model will include the factors contrast agent group and tumor classification before administration (malignant / non malignant / not assessable). The parameters of the model will be estimated using the SAS® procedure glimmix. The difference between contrast agent groups in proportions and associated 95% CI will be computed globally and for each tumor classification.

```
proc glimmix data = XXX;
  class subject GBCA tumor_cl;
  model eval = GBCA tumor_cl GBCA*tumor_cl / dist = bin link =I d ddfm = kr;
  random _residual_ / subject = patient type = cs;
  estimate "gadopiclenol - gadobutrol" GBCA -1 1 /cl;
  estimate "gadopiclenol - gadobutrol for malignant tumor" GBCA -1 1 GBCA*tumor_cl -1 0 0 1 0 0 /cl;
  estimate "gadopiclenol - gadobutrol for non malignant tumor" GBCA -1 1 GBCA*tumor_cl 0 -1 0 0 1 0 /cl;
  estimate "gadopiclenol - gadobutrol for not assessable tumor" GBCA -1 1 GBCA*tumor_cl 0 0 -1 0 0 1 /cl;
run;
```

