### **Lesion to Background Ratio (LBR)**

LBR is calculated from the SI measurement of maximum 3 most representative lesions by the 3 independent off-site readers. Then, the mean of LBR will be calculated by patient and by MRI modality using only gadopiclenol-gadobutrol matching lesions. Only pre-contrast lesions which match with those gadopiclenol-gadobutrol matching lesions will be kept in the analysis and descriptive statistics.

For each reader, LBR will be tabulated by contrast agent groups on pre contrast and paired images using FAS 2.

Differences between contrast agents will be tested using a Student's t-test. The models will include the contrast agent group, the period and the unenhanced value (pre) as covariate. The parameters of the mixed models will be estimated using the SAS® procedure Mixed. The difference between contrast agent groups in mean score and associated 95% two-sided CI will be computed.

Procedure used will be the following for each off-site reader:

```
Proc mixed data = XXX method = REML;
  class subject GBCA period;
  model eval = GBCA period pre;
  repeated GBCA/subject= subject / type = cs;
  lsmeans GBCA / pdiff = control('gadobutrol') tdiff cl alpha = 0.025;
/* The following code is needed as previous statement lsmeans does not provide the upper limit of CI */
  lsmeans GBCA;
  estimate "gadopiclenol - gadobutrol" GBCA 1 -1 /cl;
run; .
```

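### SAP 5.6.2 Number of lesions: the two count programs specify no within-patient correlation, so with positively correlated counts their intervals are too wide; the agent program also drops period

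*SAP*

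**What the plan says.** SAP 5.6.2, Number of lesions, plans two negative binomial models with an identity link, fitted separately for each off-site reader and for the on-site reading. One compares Paired with Pre images for gadopiclenol (extended FAS1). The other compares the two agents on Paired images (extended FAS2). In both, each patient contributes two counts. Both programs carry the line "random _residual_ / subject = subject", with no `type=` and no empirical variance option.

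On factors, the text says "The model will include the factors period contrast agent group and MRI modalities (pre and paired"). The agent program declares "class subject GBCA period" but then fits "model nblesions = GBCA / dist = negbin link = id". Its test is one-sided at 0.025: "lsmeans GBCA / pdiff = controlu('gadobutrol') tdiff cl alpha = 0.025". A 95% interval for the difference in mean count is also to be reported.

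Other paired secondary models in 5.6.2 do state the correlation. The treatment-plan model writes "random _residual_ / subject = patient type = cs" and the Lesion to Background Ratio model writes "repeated GBCA/subject= subject / type = cs".

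Two design facts bear on the correlation. Protocol section 7, Table 3, defines "Paired images = combined unenhanced and gadopiclenol-enhanced MRI (pre+post images"). Protocol 3.3.1 sets the two MRI visits 2 to 14 days apart in the same patient.

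At lesion level, SAP section 4 lists patient among the adjustment factors for both the plain and the lesion-size analysis. The equations and programs in 5.6.2 contain no patient term and block on lesion number only.

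**The concern.** A crossover gains precision because the patient is his or her own control. A model that gives a patient's two counts zero covariance discards that gain. The count models are the planned formal comparison of lesion detection, and Protocol 11.3.6 commits to them. An over-wide interval cannot manufacture a detection advantage, but it can hide a real difference in either direction, including fewer lesions found with gadopiclenol. A null result would then be hard to interpret.

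The period omission contradicts the SAP's own sentence. It occurs in the agent comparison, where period varies within a patient. The Paired versus Pre program does include period, although period is constant within a patient there.

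At lesion level the text names a factor that the models lack, so the two places give different instructions.

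**Working it through.** The documents give no correlation, count variance, target difference or power for lesion counts, so there is no stated figure to reproduce. The correlations below are assumptions shown as a range.

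**Counts: standard error.** Let each count have variance s², let the correlation within a patient be ρ, and let n patients contribute pairs.
- As programmed (zero covariance): Var(difference) = 2s²/n.
- True: Var(difference) = 2s²(1 − ρ)/n.
- Ratio of model SE to true SE: r = 1/√(1 − ρ), whatever the value of n.

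Derived quantities:
- Coverage of the nominal 95% interval = 2Φ(1.96r) − 1.
- Effective number of patients = n(1 − ρ), illustrated at n = 200, the evaluable-patient target in SAP section 4.
- Power for an effect that the correct analysis would detect with 80% power at one-sided 0.025 = Φ(1.96 + 0.842 − 1.96r).

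| ρ (assumed) | r | Coverage | Effective n of 200 | Power |
|---|---|---|---|---|
| 0 | 1.00 | 95% | 200 | 80% |
| 0.3 | 1/√0.7 = 1.20 | 98% | 140 | 68% |
| 0.5 | 1/√0.5 = 1.41 | 99% | 100 | 51% |
| 0.8 | 1/√0.2 = 2.24 | about 100% | 40 | 6% |

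**Unequal variances.** Negative binomial variance rises with the mean, so the two counts need not have equal variance. With variances s² and 2s², r = √[3/(3 − 2ρ√2)]. At ρ = 0.8 this is √(3/0.737) = 2.02, against 2.24 above.

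**Simulation check.** Correlated negative binomial pairs were simulated (assumed mean 2, overdispersion 0.5, 200 patients, 20,000 runs). At ρ = 0.2, 0.4, 0.6 and 0.8, model SE over true SE was 1.11, 1.28, 1.57 and 2.23; the formula gives 1.12, 1.29, 1.58 and 2.24. One-sided rejection under the null was 0.016, 0.006, 0.001 and 0.000, against a nominal 0.025. With compound symmetry, coverage was 0.946 to 0.950 and rejection 0.024 to 0.027 at every ρ.

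**Period.** With n₁ and n₂ patients in the two sequences, the unadjusted agent difference absorbs (n₁ − n₂)/(n₁ + n₂) of any period effect. At 100 v 100 this is 0. At 105 v 95 it is 10/200 = 5%.

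**Lesion level.** For a matched lesion, a score level shared by all of a patient's lesions cancels in the agent or modality difference, and the ratio of model SE to true SE is 1.00. The SE is wrong only if the differences themselves are correlated (ρd) between lesions of one patient. It is then too small by √[1 + ρd(E[n²] − E[n])/E[n]], where n here is lesions per patient, at most 3.
- All patients with 3 lesions: (9 − 3)/3 = 2, giving 1.10, 1.26 and 1.41 at ρd = 0.1, 0.3 and 0.5.
- 70/20/10% with 1/2/3 lesions: (2.4 − 1.4)/1.4 = 0.714, giving 1.04, 1.10 and 1.17.
- Single lesions only: 1.00.

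The SAP also keeps unmatched lesions in these models. In the scenarios run (up to 40% affected), a shared patient level alone then moved coverage by about one percentage point or less, in either direction.

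**The case against.** The strongest reply is that SAP code is a template. Several programs would not run as printed; the primary models, for example, have a second slash before `type = cs`. A missing option is one more slip, and its meaning rests on a SAS default (TYPE=VC) that the documents do not state. This is fair as to weight. It does not remove the point: elsewhere the intended correlation can be read despite the syntax, and here nothing states one.

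On period, the intent is written in the text and randomization is 1:1 in blocks (Protocol 5.3.1). What remains is a code slip with little or no bias.

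A reader might infer that the faulty code drives all eight negative binomial tables and the four count forest plots. The documents do not support that. For body region and organ, the SAP prints no count code and refers to the subgroup section, where the models use compound symmetry by patient and include period. The printed programs are tied only to Tables 14.2.2.23, .25, .27 and .29 and to no forest plot. What is open is how the subgroup structure carries into a negative binomial model.

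A reader might also infer that the lesion-level intervals are too narrow because patient is missing. For matched lesions that needs correlated differences, which the documents do not show, and an additive patient factor as named in SAP section 4 would not cure it.

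Finally, the 6% power figure needs a correlation of 0.8 and an effect scaled to 80% power. It is the far end of a range, not a forecast.

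**Conclusion.** The count code is wrong as written, in a conservative direction. Its size depends on an unknown correlation: none at zero, and an SE inflated by 1.20 to 2.24 over 0.3 to 0.8 with equal variances. The conclusion rests on the GLIMMIX default and on positive correlation, which the shared Pre images and shared patients make likely but which the documents do not quantify. The missing period term is a plain conflict between text and code, without bias when the sequences are equal.

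The lesion-level mismatch is real but minor and conditional; no harm is shown. Only secondary analyses are touched. Both primary models in SAP 5.6.1 block on patient with compound symmetry. Low severity.

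**What to change.** - In both count programs write `random _residual_ / subject=subject type=cs`, with a patient-clustered empirical standard error as fallback if the model does not converge.
- Add period to the MODEL statement of the agent program.
- Add a sentence confirming that the body-region and organ count models keep the compound-symmetry and period structure of the subgroup section.
- Align SAP section 4 with the lesion-level and lesion-size models by using a patient-clustered standard error, and make lesion number unique across patients.

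The cost is SAP text and code edits only, with no new data. Count intervals narrow if the counts are positively correlated. Lesion-level intervals may widen; with matched lesions they stay essentially the same if a patient's lesion differences are uncorrelated, and change little if most patients have one lesion.
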